#### 5.9.2 Termination of Clinical Study

If the PI, the Sponsor or the Medical Monitor becomes aware of conditions or events that suggest a possible hazard to patients if the clinical study continues, the clinical study may be terminated after appropriate consultation among the involved parties, the Sponsor or Principal Investigator (PI) or the regulatory authorities or Independent Ethics Committee/Institutional Review Board (IEC/IRB). Also, the clinical study may be terminated at the Sponsor's discretion in the absence of such a finding.

Conditions that may warrant termination of the clinical study include, but are not limited to:

- The discovery of a relevant unexpected or unacceptable risk to the patients enrolled in the clinical study;
- Three patients develop the same AE of CTCAE Grade 3;
- OR two patients develop any AE of CTCAE Grade 4;
- OR one patient develops an AE of CTCAE Grade 5;
- Failure to enroll patients at the required rate;
- A decision of the Sponsor to suspend or discontinue development of the study drug. Should the study be terminated and/or the site closed for whatever reason, all documentation pertaining to the study and IP must be returned to the Sponsor. Any actions of the Contract

CONFIDENTIAL
PAGE 40 OF 80

Research Organization required for assessing or maintaining patient safety will continue as required, despite termination of the study by the Sponsor.

#### 5.10 RESTRICTED MEDICATIONS

- Patients are not permitted to take zileuton, vitamin E (>400 IU/day) or other drugs with potential effect on NAFLD/NASH such as ursodeoxycholic acid, Sadenosylmethionine (SAM-e), betaine, pentoxifylline.
- Patients are not permitted to take thiazolidinediones (pioglitazone, rosiglitazone), chemotherapy or other investigational medications during the study duration.
- Concomitant use of strong CYP2C8 Inhibitors/Substrates will be prohibited.
- Patients also should not take any non-allowed over-the-counter medications or complementary and/or alternative medications.

No incidence of overdose with Saroglitazar magnesium has been reported. In case of overdose

with Saroglitazar magnesium, general supportive care of the patient is indicated, including

### 5.11 OVERDOSE AND DRUG INTERACTION

monitoring of vital signs and observation of clinical status.

Approved by: [name] [name] Protocol No.: SARO.17.010

CONFIDENTIAL
PAGE 41 OF 80

#### 5.12 TREATMENT COMPLIANCE

The patients will be asked to bring their bottles of the IP to the next visit; compliance for dosing will be assessed by examination of the bottles and tablet count by study personnel. Compliance will be documented on Individual drug accountability log(s). Study medication compliance <80% or >120% will be considered protocol deviations and require patients to be counselled on proper IP compliance.

Approved by: [name] [name] Protocol No.: SARO.17.010

CONFIDENTIAL
PAGE 42 OF 80

### 6 OBSERVATIONS

#### 6.1 SAFETY

### 6.1.1 Primary Endpoint

The primary endpoint is to assess the safety of Saroglitazar magnesium 4 mg tablets in liver transplant recipients with NAFLD over 24 weeks of treatment.

Safety will be assessed during the study period through the reporting of AEs, and by clinical laboratory tests and vital sign assessment at various time points during the study.

### 6.1.2 Medical History and Demographic Information

The medical history comprises:

- Complete medical history
- Medication history
- Reproductive history

The following demographic information will be recorded:

- Gender
- Age
- Ethnic origin
- Race
- Height, without shoes
- Body weight, without shoes
- BMI

#### 6.1.2.1 Vital Signs

The following vital signs will be assessed at time points described in the Schedule of Assessments (Table 1):

- Sitting BP (systolic and diastolic; mmHg)
- Pulse (beats per minute)
- Oral body temperature (°F)
- Respiratory rate (breaths per minute).

Vitals signs will be measured before any blood draw that occurs at the same visit and after the patient has been resting for at least 5 minutes.

Approved by:	Protocol No.: SARO.17.010
[name] [name]	Version No.: 7.0

CONFIDENTIAL
PAGE 43 OF 80

#### **6.1.2.2** Physical Examinations

Physical examination will be performed in accordance with the Schedule of Assessments (Table 1). The physical examination will consist of an evaluation of the head, neck, eyes, ears, nose, throat, chest, heart, lungs, abdomen, skin, extremities, and the neurological and musculoskeletal systems.

Patients' body weight will be recorded during all physical examinations. Height will be recorded at Screening Visit only.

### **6.1.3** Clinical Laboratory Assessments

All biological samples, with the exception of pharmacokinetic samples will be assayed at Institution laboratory by using analytical methods in compliance with standard and validated methodologies, with adherence to written standard operating procedures (SOPs) of the Institution throughout the study duration.

If multiple bioanalytical assay methods/local laboratories will be used, then cross-comparison among methods shall be performed to allow comparison of efficacy and safety parameters/values obtained by different assay methods. All laboratory tests done at the local laboratory will be per the site's policies and SOPs.

Details regarding the sample processing, handling, storage, and shipment of PK samples will be offered separately in the study-specific laboratory manual prior to the initiation of the trial.

#### **6.1.3.1** Sample Collection

The total amount of blood drawn for each patient over the study will not exceed 500 mL. Multiple venipunctures should be avoided to collect blood samples. It is recommended to collect only 1 blood sample for efficacy and safety measurement at a given visit. Blood samples will be collected for clinical laboratory testing at the time points indicated in the Schedule of Assessments (Table 1). Safety laboratory variables are listed in below mentioned Table 3.

**Table 3: Safety Laboratory Assessments** 

Hematology	Hematocrit, hemoglobin, MCHC, MCV, platelet count, MPV, RBC count, WBC count, differential WBC count
	Coagulation Panel: APTT, PT/INR ratio, TT.

Approved by:	Protocol No.: SARO.17.010
[name] [name]	Version No.: 7.0

CONFIDENTIAL
PAGE 44 OF 80

_, ,	O/ 11 (0 1 1 1 1 0 1 0		
	Liver function tests: AST, ALT, ALP, total bilirubin (with Conjugated		
	bilirubin), GGT, total protein and albumin		
	Amylase and lipase		
	Renal function tests: BUN, serum creatinine, eGFR		
	eGFR will be calculated by using Chronic Ki		
	Epidemiology Collaboration (CKD-EPI) equa		
	Creatine phosphokinase, CK-MB, troponin 1 and NT		
	Serum electrolytes: sodium, potassium, calcium, bica		
	Gut hormones: Ghrelin, glucagon like peptide, leptin,	resistin, and	
	adiponectin		
	HbA1c and fasting plasma glucose		
8.	HIV type 1 and type 2 HAV IgM,		
	HBsAg		
HCV Immunosuppression level (tacrolimus, cyclosporine or			
		sirolimus)	
	CMV (IgG), and EBV VCAIgG		
•	Physical examination (appearance, color, specific gravity and pH); microscopy (epithelial cells, red blood cells, pus or white blood cells, casts and crystals) and chemical examination (protein, glucose, bilirubin, urobilinogen, ketone bodies, nitrite and blood) Urine drug testing		
	Serum pregnancy test for women of childbearing poter Visit 1, and Visit 8.	ntial at the Screening	
	Urine pregnancy test will be performed on Visit 2 to7	and Visit 9.	

### 6.1.4 Twelve-lead Electrocardiograms and 2D ECHO

A standard 12-lead electrocardiogram will be performed locally at the study site in accordance with the Schedule of Assessments (Table 1). Twelve-lead electrocardiogram recordings will be taken in triplicate at the Screening Visit and as a single recording at all other applicable visits. A 5-minute rest period in between vital signs and ECG measurements is recommended. A 2D ECHO will be performed at baseline and end of the treatment visit.

#### 6.1.5 Adverse events

Adverse event reporting will begin after the informed consent has been signed and will continue until end of follow-up period. The Common Terminology Criteria for Adverse Event (CTCAE) (Version 4.03 or higher) system will be used for reporting and grading AEs. Please refer Section 9.4 for details description.

All AEs will be captured in the AE eCRF. At a minimum, SAEs will be reported in the eCRFs as per the timelines defined in the Protocol in adverse event section.

Serious adverse events reporting must comply with the concerned regulatory requirements and IEC/IRB reporting requirements.

Approved by:	Protocol No.: SARO.17.010
[name] [name]	Version No.: 7.0

CONFIDENTIAL

**PAGE 45 OF 80** 

Every effort should be made to ensure that the protocol required tests and procedures are completed as described. However, it is anticipated that from time to time there may be circumstances, outside of the control of the PI that may make it infeasible to perform the test. In these cases, the PI will take all steps necessary to ensure the safety and well-being of the patient. When a protocol required test cannot be performed the PI will document the reason and the corrective and preventive actions which he/she has taken to ensure that normal processes are adhered to as soon as possible. The study team will be informed of these incidents in a timely fashion.

#### **6.2 EFFICACY**

Efficacy will be assessed through a number of exploratory endpoints.

- 1 Changes in hepatic fat as determined by MRI-PDFF and MRE from baseline to EOT.
- 2 Changes in metabolic flexibility from baseline to EOT.
- 3 Changes in markers of insulin resistance FSIVGTT, HbA1c and fructosamine from baseline to EOT.
- 4 Changes in serum liver enzymes from baseline to EOT.
- 5 Changes in serum lipids from baseline to EOT.
- 6 Changes in atherogenic lipoprotein which includes sdLDL, LDL size and concentration, subtypes of VLDL and HDL from baseline to EOT.
- 7 Change in QoL score from baseline to EOT.
- 8 Pharmacokinetics of Saroglitazar following first dose and last dose in liver transplant recipients with nonalcoholic fatty liver disease.
- 9 Body composition assessment via change in adipose tissue and skeletal muscle volume from baseline to EOT by whole body MRI.

### **6.2.1** Magnetic Resonance Imaging-Derived Proton Density-Fat Fraction (MRI-PDFF)

The magnetic resonance imaging-estimated proton density fat fraction (MRI-PDFF) is a novel imaging-based biomarker that allows fat mapping of the entire liver. Liver fat content will be measured using MRI-PDFF. Proton-density-fat-fraction technique is an MRI protocol that improves on the conventional Dixon in- and out-of phase method. PDFF uses a low flip angle to reduce T1 bias (Bydder M et al. 2008; Liu et al. 2007). Multiple echoes per excitation are used to correct T2\* decay (Bydder M et al. 2008; Yokoo et al. 2009; Yu et al. 2007). As a

PAGE 46 OF 80

result, the expected loss of signal with longer echo times, particularly in the presence of iron, is corrected. In head-to-head comparisons, PDFF quantified liver fat more accurately than conventional two-point Dixon MRI (Yokoo et al. 2011; Mashhood et al. 2013). In addition, PDFF minimizes the multifrequency interference effects of fat protons (Yokoo et al. 2009). PDFF has been shown to have high reproducibility at 1.5 T and 3.0 T (Kang et al. 2011). Studies assessing liver fat have confirmed the accuracy of PDFF using hydrogen-1 MR spectroscopy (H1-MRS) (Yokoo et al. 2009; Yokoo et al. 2011; Kang et al. 2011; Noureddin et al. 2013) or liver histology (Idilman et al. 2013; Tang et al. 2013) as gold standard. In addition, PDFF MRI technique allows fat mapping for the entire liver, whereas longitudinal segmental changes of liver fat may be accurately determined and small differences can be detected (Noureddin et al. 2013). The procedure will be conducted per the site's policies and SOPs for the procedure which will be followed for the study.

### **6.2.2** Controlled Attenuation Parameter (CAP)

[figure not shown]
CAP based on FibroScan is a promising tool for noninvasive semiquantitative assessment of liver fat content (*De Ledinghen V, 2012*). CAP measures the ultrasound attenuation at the center frequency of the FibroScan M probe (3.5 MHz), with values range from 100 to 400 dB/m. Besides CAP being able to provide an instantaneous assessment of liver steatosis, some advantages, such as quantificational accuracy and ease of performance (which provide for instantaneous results), as well as inexpensive cost and reproducibility are highlighted when compared with other imaging methods (*De Ledinghen V et al, 2014*). In a prospective study of 153 patients, the areas under the receiver operating characteristics curves of CAP for  $\geq$ 5%,  $\geq$ 33% and  $\geq$ 66% steatosis were 0.79, 0.76 and 0.70, respectively (*Myers RP et al, 2012*).

See below table for vibration-controlled transient elastography cutoff values for CAP (Siddiqui et. al. CGH 2019). This table indicates 263 dB/m cutoff value to optimize sensitivity.

Steatosis grade: Non-event vs event	Prevalence of event	Cross- validated AUROC (95% CI)	Cut-off criteria	Cut-off (dB/m)	Sens	Spec	PPV	NPV
0 vs 1-3	95%	0.76 (0.64, 0.89)	Sens = 90%	263	0.90	0.35	0.96	0.15
			Spec = 90%	353	0.29	0.90	0.98	0.06
			Youden's index	285	0.80	0.77	0.99	0.16

Approved by:
[name] [name]

Protocol No.: SARO.17.010

### 6.2.3 Magnetic Resonance Elastography (MRE)

Magnetic resonance elastography (MRE) is a dynamic elasticity imaging technique that uses mechanical waves to quantitatively assess the shear modulus or stiffness of tissues (Muthupillai et al., 1995).

The three basic steps of this MRE are i) shear waves with frequencies ranging from 50 - 500 Hz are induced in the tissue using an external driver, ii) the waves are imaged inside the body using a special MRI technique and iii) the resulting data are processed to generate quantitative images displaying the stiffness of tissue. The procedure will be conducted per the site's policies and SOPs for the procedure which will be followed for the study.

#### 6.2.4 Whole Body MRI

Body composition is linked to cardiometabolic health and will be evaluated in patients. Subjects will be scanned in a research-dedicated Phillips Ingenia 3.0T Omega HP Multi-Transmit MRI scanner using 6-minute dual-echo Dixen Vibe protocol, providing a water and fat separated volumetric data set covering neck to knees. Acquired images will be analyzed for visceral adipose tissue, subcutaneous adipose tissue, thigh muscle volume, and muscle fat infiltration in the anterior thighs. Liver fat content will be quantified via proton density fat fraction as published previously (Linge et. al, 2018).

### **6.2.5** Frequently Sampled Intravenous Glucose Tolerance Test (FSIVGTT)

The Frequently Sampled Intravenous Glucose Tolerance Test assesses insulin sensitivity by a computed mathematical analysis of glucose and insulin dynamics. FSIVGTT consists of an intravenously administered bolus of glucose and an infusion of insulin 20 minutes after

Approved by:	Protocol No.: SARO.17.010
[name] [name]	Version No.: 7.0

CONFIDENTIAL
PAGE 48 OF 80

glucose injection. Blood samples are collected periodically for total test duration of 120 minutes. The procedure will be performed as per Institution standard operating guideline.

#### 6.2.6 Metabolic Flexibility

**Energy expenditure:** The recording of the components of energy balance, i.e. energy intake and expenditure is extremely important to understand the individual's response to pharmacologic or lifestyle modifications interventions. Yet, estimation of energy expenditure by equations, and food dietary recording are imprecise and subject to recall bias, respectively. The indirect calorimetry technique, by measuring the oxygen consumption allows a precise measurement of energy expenditure; additionally, the measurement of carbon dioxide production provides the opportunity of measuring the respiratory quotient (RQ) and in turn calculating the substrate utilization (carbohydrate vs. fat). Virginia Commonwealth University has a newly established indirect calorimeters suite with two whole room indirect calorimeters, a small 4'x8' "flex room" for short term studies and a larger 10'x10' room, fitted with hospital bed, sink, and toilet which allows long-term studies. Additionally, recent improvements in the data acquisition algorithm allow the recording of acute changes in energy expenditure. By coupling minute by minute measurements of energy expenditure with wearable sensors able to capture spatial movements, researchers have the unique opportunity to precisely measure the energy expenditure in its components. Finally, by providing study meals with known calorie content and macronutrient composition researchers are also able to control the energy intake arm of the energy balance equation (Galgani and Ravussin, 2008).

**Metabolic Flexibility**: The switch from carbohydrate oxidation to lipid oxidation defined as a drop in RQ during an overnight fasting is one of the gold-standard measures to assess metabolic flexibility. Insulin-resistant and T2DM patients are characterized by a metabolic inflexibility, which is associated with even worse insulin resistance, and they typically present with an impaired drop in RQ overnight (higher RQ), defining metabolic inflexibility, and specifically metabolic inflexibility to lipids. A significant change in mean 14-hour RQ, as well as changes of the RQ area under the curve between baseline and the end of the intervention would suggest improvements in metabolic flexibility, which is associated with improved metabolic outcomes (Goodpaster and Sparks, 2017; Galgani et al., 2008).

Protocol No.: SARO.17.010

CONFIDENTIAL
PAGE 49 OF 80

### 6.2.7 Quality of Life Assessment

### 6.2.7.1 SF-36 Health Survey

Subjective QoL assessments will be measured using the SF-36 version 2.0, which is a 36-item patient response questionnaire that measures QoL across 8 domains, both physically and emotionally based. The 8 domains are physical functioning, role limitations due to physical health, role limitations due to emotional problems, energy/fatigue, emotional well-being, social functioning, pain and general health.

For information about the quality of life assessment, SF-36, version 2, refer to the SF-36.org Community at http://www.sf-36.org/tools/sf36.shtml.

### 6.2.8 Pharmacokinetics Assessment

Pharmacokinetics of Saroglitazar will be assessed following first dose and last dose in liver transplant recipients with NAFLD. The samples will be collected at Pre-dose (0.0), 0.5, 1.0, 2.0, 3.0, 4.0, 6.0, 8.0, 10.0 and 24 hours post-dose. In addition, pre-dose sample will be collected at Visits 3, 4, 5, 6 and 7. The sampling will be performed only in approximately 5 patients participating in the PK evaluation. A separate PK manual will be created describing the detailed procedures for PK sample handling, storage, shipment, bioanalysis, quality oversight and reporting of data.

The following pharmacokinetic parameters will be evaluated for first and last dose:

- a. Peak plasma concentration (Cmax)
- b. Time to reach peak plasma concentration (Tmax)
- c. Area under plasma concentration vs. time curve till the last time point (AUC0-t)
- d. Area under plasma concentration vs. time curve extrapolated to the infinity (AUC0- $\infty$ ) after first dose
- e. Area under plasma concentration vs. time curve in a 24 h dosing interval (AUCtau)
- f. Elimination rate constant  $(\lambda z)$
- g. Elimination half-life (t1/2)
- h. Apparent volume of distribution (Vd/F)
- i. Apparent clearance (CL/F)
- j. Minimal or trough plasma concentration (Cmin) -for last dose only
- k. Accumulation index calculated as a ratio of AUCtau (last dose)/AUCtau (first dose)

CONFIDENTIAL PAGE 50 OF 80

Fluctuation index

#### 6.2.9 Appropriateness of Measurement

The endpoints chosen for the given study [safety and efficacy] are appropriate for the assessment of outcome of the study.

#### 6.2.10 Abnormal Laboratory Findings

In addition, a clinically significant value outside the normal or reference range in a routine safety assessment, such as clinical laboratory, vital signs or standard 12-lead ECG, and 2D ECHO may signify an adverse finding. Additional examinations or repetition of test will be performed as medically indicated.

If the PI considers the abnormality as of major medical relevance, he/she should also record this as an AE. If the findings contribute to a clinical diagnosis (e.g. hepatitis in case of increased liver enzymes), this diagnosis should be recorded as an AE.

The criteria for determining whether an abnormal objective test finding should be reported as an AE are as follows:

- 1. The test result is associated with accompanying symptoms, and/or
- 2. The test result requires additional diagnostic testing or medical/surgical intervention, and/or
- 3. The test result leads to change in study dosing or discontinuation from the study, significant additional concomitant drug treatment or other therapy, and/or
- 4. The test result leads to any of the outcomes included in the definition of an SAE, and/or
- 5. The test result is considered to be an AE by the PI or designee.

For any abnormal test result that meets one of the above conditions except for the last condition, the PI or designee will provide a justification in the source documentation for not reporting the abnormal test finding as an AE.

Each AE shall be evaluated for severity, seriousness, duration, resolution, action taken and its association with the study treatment. The participant may be withdrawn or terminated from the study depending on the seriousness of the AE(s).

CONFIDENTIAL
PAGE 51 OF 80

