#### 9.4 PROCEDURES

#### 9.4.1 Adverse Events

All AEs occurring during the course of the clinical trial from the signing of the informed consent onwards will be collected, documented, and reported to the Sponsor by the PI or designee according to the specific definitions and instructions detailed in this section.

An AE is defined as any untoward medical occurrence in a clinical investigation subject administered a pharmaceutical product and which does not necessarily have a causal relationship with this treatment.

Any medical condition already present at screening should not be reported as an AE unless the medical condition or signs or symptoms present at baseline changes in severity or seriousness at any time during the study. In this case, it should be reported as an AE.

PAGE 67 OF 80

Clinically significant abnormal laboratory or other examination (e.g. electrocardiogram) findings that are detected during the study or are present at screening and significantly worsen during the study should be reported as AEs. The PI will exercise his or her medical and scientific judgment in deciding whether an abnormal laboratory finding or other abnormal assessment is clinically significant. Clinically significant abnormal laboratory values occurring during the clinical study will be followed until repeat tests return to normal, stabilize, or are no longer clinically significant. Any abnormal test that is determined to be an error does not require reporting as an AE.

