#### Serious Adverse Event Reporting-Procedures for Investigator:

#### **Initial Reports:**

Any SAE, or follow-up to a SAE, including death due to any cause that occurs to any subject from the time the consent is signed through 4-week following cessation of treatment, whether or not related to the Sponsor's product, must be reported to the Sponsor within 24 hours of the knowledge of the occurrence to investigational site.

Additionally, any SAE, considered by the PI or designee, who is a qualified physician, to be related to the Sponsor's product, that is brought to the attention of the PI or designee at any

[figure not shown]

CONFIDENTIAL PAGE 68 OF 80

time outside of the time-period specified in the previous paragraph also must be reported immediately to the Sponsor.

To report an SAE, complete the SAE form electronically in the electronic data capture (EDC) system for the study. Once the form is completed, the CRO/Sponsor Safety personnel will be notified electronically. If the event meets serious criteria, and, it is not possible to access the EDC system, send an email to CRO/Sponsor or call the CRO/Sponsor SAE hotline (phone number listed below), and email the completed SAE form/information to CRO/Sponsor (email listed below) within 24 hours of awareness. When the EDC system becomes available, the SAE information must be entered within 24 hours of the system becoming available.

Safety Contact Information:

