### 8.3.2 Adverse Events

The applicable definition of an Adverse Event (AE) is in the study protocol section 9.4. A treatment-emergent AE (TEAE) is an event not present prior to exposure to study drug or any pre-existing event that worsens following exposure to study drug. The period for treatment-emergent AE analysis starts from the first exposure to the study drug until the patient exits the study.

Descriptive summaries (frequencies and percentages) for specific TEAEs will be presented by system organ class and preferred term according to the Medical Dictionary for Regulatory Activities (MedDRA Version 21.0) dictionary. In addition to an overall presentation of all TEAEs, reports will be generated for special classes of TEAEs such as drug related TEAEs, serious TEAEs, Maximum severity and TEAEs resulting in treatment discontinuation. These reports will be supported by individual patient listings, as necessary.

Adverse events will be counted by the number of events as well as the number of patients. For the summaries which count the number of patients, multiple TEAEs with the same MedDRA preferred term within the same patient will only be counted once.

Only patient listings will be provided for AEs that occur after signing informed consent but prior to exposure to study drug. These listings will comprise all events occurring during this period in any patient who consented to participate in the study.

These listings will at least contain but not limited to information such as onset and resolution times, maximum severity, causal relationship to study drug and action taken.

Statistical Analysis Plan			
Version Number:	1.0	Date:	31 Dec 2021
Protocol Number:	SARO.17.010	Sponsor Name:	Zydus Therapeutics Inc.

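### Protocol 6.2.10 lets an abnormal test that led to a dosing change or discontinuation go unrecorded as an AE on a source note alone, so laboratory-driven drug stops can be missing from the AE-based safety outputs

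*Protocol*

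**What the plan says.** Protocol 6.2.10 sets five criteria for reporting an abnormal objective test as an AE. Criterion 3 reads in part "The test result leads to change in study dosing or discontinuation from the study". Criterion 4 reads "The test result leads to any of the outcomes included in the definition of an SAE". Criterion 5 is that the PI or designee considers the result an AE.

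For any result that "meets one of the above conditions except for the last condition", the section continues, "the PI or designee will provide a justification in the source documentation for not reporting the abnormal test finding as an AE". The same section says that a clinical diagnosis to which the findings contribute should itself be recorded as an AE.

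Protocol 9.4.1 says clinically significant laboratory findings should be AEs, but leaves significance open: "The PI will exercise his or her medical and scientific judgment in deciding whether an abnormal laboratory finding" is clinically significant. It gives two limits: a condition already present at screening counts only if it changes in severity or seriousness, and "Any abnormal test that is determined to be an error does not require reporting as an AE".

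Protocol 9.4.2 defines an SAE as a kind of AE. Any SAE, related or not, "must be reported to the Sponsor within 24 hours of the knowledge of the occurrence to investigational site".

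Protocol 5.9.1 item 2 requires study drug to be stopped on laboratory limits and does not say that such a stop is to be entered as an AE. SAP 8.3.2 lists, among its special reports, "TEAEs resulting in treatment discontinuation".

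**The concern.** Safety is the primary endpoint, the trial is open-label with a single arm of 15 patients, and the primary analysis in Protocol 8.2.2 consists of AE listings and AE summaries. Whether an event is entered as an AE therefore decides whether it reaches the main output.

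The clause in 6.2.10 leaves that decision to the site for a class of results that by definition had consequences for treatment. The only stated condition is a note in the source documents. No eCRF entry is required, and no review of the note by the sponsor or the DMC is specified. If it is used for laboratory-driven stops, the trial could report few or no discontinuations due to AEs while patients did stop the drug on safety limits.

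**Working it through.** The plan states no figure on this point, so there is none to reproduce. The check is mainly a comparison of passages, followed by short arithmetic.

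**1. Scope of the clause.** Five criteria less the last leaves criteria 1 to 4. A drug stop under 5.9.1 is a change in study dosing, so it falls under criterion 3.

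**2. Does another section force an AE entry?**
- 9.4.1 would do so for a clinically significant finding, but the PI decides significance.
- 6.2.10 would do so where there is a clinical diagnosis. An isolated laboratory value crossing a limit need not yield one.
- 9.4.2 would do so for an SAE. Because an SAE is defined there as an AE, a result left out of the AE record under criterion 4 sits awkwardly with that duty, and 6.2.10 does not say which prevails.
- 5.9.1 does not.

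For criterion 3 the gap is open. For criterion 4 it is an ambiguity.

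**3. Are laboratory-driven stops foreseeable?** In 5.9.1 item 2, limits a to e are laboratory values (bilirubin, CK, amylase or lipase, eGFR, haematology), with renal replacement therapy the one addition. Entry limits lie close to some of them. Exclusion 17f in 4.3 and stop limit 2d both use eGFR 60 mL/min/1.73 m². Exclusion 17a removes WBC below 2.5 × 10³/µL, while limit 2e stops drug below 4 × 10³/µL.

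**4. Outputs that depend on an AE entry.**
- Protocol 8.2.2: primary AE listings and summaries.
- Protocol 3.3: dropouts due to AEs or SAEs.
- SAP 8.3.2: TEAEs leading to discontinuation.
- Protocol 5.9: three or more subjects with the same related SAE.
- Protocol 5.9.2: three patients with the same Grade 3 AE, two with any Grade 4, or one with Grade 5.
- Protocol 7.5: the DMC counts by grade.

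**5. Outputs that do not.** By-visit abnormal laboratory tables (Protocol 8.2.3), laboratory summaries, the shift table and listings (SAP 8.3.5), and disposition (SAP 5). Two are weaker than they look. Disposition counts discontinuation from the study, whereas 5.9.1 concerns stopping the drug. The shift table compares baseline with the last study visit, by which time a value followed to resolution may have returned. Neither document plans a table of drug stops by laboratory criterion.

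**6. Effect on a percentage.** With n = 15, one patient is 1/15 = 6.7 points. Suppose two or three patients stop on a laboratory limit. The true figures are 2/15 = 13.3% and 3/15 = 20.0%. If none were entered as an AE, the table would show 0/15. Exact 95% intervals: 0/15 gives 0 to 21.8%; 3/15 gives 4.3 to 48.1%.

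**7. Effect on a count trigger (illustration only).** Let p be the chance that a patient has an event that would count, and s the share of such events not entered as AEs. Both are assumed; neither is in the documents. The recorded number is binomial(15, q) with q = p(1 − s), and a trigger needing at least three patients fires with probability P(X ≥ 3). For p = 0.20 and s = 0: 1 − [0.8¹⁵ + 15(0.2)(0.8¹⁴) + 105(0.2²)(0.8¹³)] = 1 − (0.035 + 0.132 + 0.231) = 0.602.

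| p | s = 0 | s = 25% | s = 50% |
|---|---|---|---|
| 0.10 | 18.4% | 9.7% | 3.6% |
| 0.20 | 60.2% | 39.6% | 18.4% |
| 0.30 | 87.3% | 69.0% | 39.6% |
| 0.40 | 97.3% | 87.3% | 60.2% |

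The documents do not map the 5.9.1 limits to CTCAE grades, so the share of laboratory stops that would count towards a Grade 3 or 4 trigger is unknown.

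**The case against.** The strongest reply is that the clause is narrow in practice and other routes catch what matters.

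- **Oversight.** A reader might infer that a stop left out of the AE record is invisible to every safety trigger. The documents do not support that. Section 5.9 evaluates safety on laboratory changes as well as AEs and lets the PI halt on an adverse trend. Section 5.9.2 allows termination for an unacceptable risk without any count. Section 7.5 has the DMC review safety data regularly. Only the numeric triggers are exposed.
- **SAEs.** A reader might infer that 6.2.10 waives SAE reporting. It does not: the clause concerns the test finding, a resulting diagnosis should still be recorded, and 9.4.2 covers any SAE, including death. What stands is that 6.2.10 is silent on precedence.
- **Legitimate use.** The clause can prevent double entry, for example raised enzymes alongside hepatitis already recorded. It also fits a stable abnormality present at entry: a patient enrolled with WBC 3.0 × 10³/µL meets the 5.9.1 limit with no change, and 9.4.1 would not call that an AE. This stands, and it means that test error cannot be the only exception.
- **Visibility.** Section 6.1.1 assesses safety by laboratory tests and vital signs too, the laboratory outputs remain, and monitors check eCRF data against source. This stands, but none of it puts a drug stop into the AE tables or names the limit that caused it.

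**Conclusion.** The point holds for criterion 3, and more weakly, as an unstated precedence, for criterion 4. As written, 6.2.10 allows a laboratory-driven drug stop to be absent from the primary AE summaries, the SAP discontinuation report and the numeric AE/SAE-count triggers. The SAE count in 5.9 is the least exposed, since 9.4.2 still applies.

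The size cannot be estimated. Neither the number of laboratory stops nor the use of the clause is given. A reader might take 0% in place of 6.7% to 20.0% as an expected bias. It is the extreme case of one to three such stops with the clause used every time. The trigger probabilities likewise rest on assumed p and s. What is certain is the granularity: 6.7 points per patient in the primary safety output. This is a reporting rule worth tightening because tightening is cheap. It does not show that safety monitoring as a whole fails.

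**What to change.** **Protocol 6.2.10 and eCRF instructions.** Require a result meeting criterion 3 or 4 to be recorded as an AE unless one of these applies:
- it is a confirmed test error (as in 9.4.1);
- it was present at screening and has not worsened (as in 9.4.1);
- it is already covered by a diagnosis recorded as an AE.

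State that 6.2.10 does not override the 24-hour SAE rule in 9.4.2.

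**SAP.** Add one table or listing of all study-drug discontinuations by reason, naming the 5.9.1 laboratory criterion met, whatever the AE status. This presumes that the reason for stopping drug is captured, which the documents do not show.

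**Reconcile.** The sponsor should reconcile the differing WBC limits in 4.3 and 5.9.1. No threshold is proposed here.

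**Cost.** A few sentences, one extra output, and slightly more AEs recorded. No clinical rule changes.
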